9.4. Other Secondary Endpoints Analysis

Continuous endpoints (HbA1c, FPG, body weight, systolic blood pressure and diastolic blood pressure) will be analyzed using a constrained longitudinal data analysis (cLDA) model including fixed effects for treatment (categorical), visit (categorical), and treatment by visit interaction. This model assumes a common mean across treatment groups at baseline and a different mean for each treatment at each of the post-baseline time points. In this model, the response vector consists of baseline and the values observed at each post-baseline time point. Time is treated as a categorical variable so that no restriction is imposed on the trajectory of the means over time. No explicit imputation of missing assessments will be performed. The treatment difference in terms of mean change from baseline to the relevant

time points of interest will be estimated and tested from this model using least-squares means and 95% confidence intervals. An unstructured covariance matrix will be used to model the correlation among repeated measurements. The Kenward-Roger adjustment will be used with restricted (or residual) maximum likelihood (REML) to make proper statistical inference. Descriptive and graphical summaries by treatment group and time point will also be presented. Other continuous endpoints will be summarized with descriptive statistics by treatment and time.

Dichotomous endpoints such as the proportion of subjects having an HbA1c <7% (53 mmol/mol) at specified time points, will be analyzed using a logistic regression model with terms for treatment (categorical) and baseline HbA1c (continuous). Summary measures from the analysis will include the odds ratio and 95% confidence interval for the odds ratio. Other dichotomous endpoints will be summarized descriptively with numbers and percentages by treatment and time.

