meta-analysis, provided in the initial registration dossier, to support the cardiovascular safety of ertugliflozin. The endpoint for the meta-analysis will be MACE plus. The goal of this meta-analysis will be to rule out a hazard ratio of 1.8 (an 80% increase in the risk of MACE plus relative to a non-ertugliflozin comparator group).

This trial will continue in the post-approval period to assess the primary endpoint of time to the first occurrence of the composite endpoint of MACE as well as other secondary endpoints. The study's primary hypothesis of non-inferiority of ertugliflozin to placebo will be evaluated by excluding a hazard ratio of 1.3 (a 30% increase in the risk of MACE relative to placebo). If non-inferiority at the 1.3 margin is established for the primary MACE endpoint, then tests of superiority on the secondary endpoints of cardiovascular death or hospitalization for heart failure (composite) and cardiovascular death (individual component) will also be performed. As stated before, this trial is event-driven, with the number of events required to occur prior to assessment of the study's primary endpoint discussed in [Sections 3.1](#) and [9.1](#).

Beyond the effects on cardiovascular endpoints, the trial is also designed to assess the safety and tolerability of ertugliflozin and its effects on measures of glycemic control, blood pressure, body weight, renal function and albuminuria.

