1.2.2. Safety of Ertugliflozin and SGLT2 Inhibitors

The SGLT2 inhibitors dapagliflozin, canagliflozin and empagliflozin are approved in the US and in the European Union. Based on available clinical trial data with dapagliflozin, canagliflozin and empagliflozin, several potential risks from SGLT2 inhibition have been identified. In clinical trials, the rate of genital fungal infections in males and females has consistently been higher in subjects receiving SGLT2 inhibitors as compared to placebo or other diabetes medications. Therefore, the increased risk of genital fungal infections can be considered a class effect of SGLT2 inhibitors. Glucosuria can potentially result in increased risk of urinary tract infection (UTI) and this adverse drug reaction was commonly reported in clinical trials with marketed SGLT2 inhibitors. Most infections were mild to moderate in severity and infections were reported more frequently in females than in males. There have also been postmarketing reports of serious UTIs including urosepsis and pyelonephritis requiring hospitalization in patients receiving marketed SGLT2 inhibitors.

SGLT2 inhibition results in an osmotic diuresis, which may lead to reductions in intravascular volume and a small decrease in blood pressure. In clinical trials with marketed SGLT2 inhibitors, treatment was associated with an increase in the incidence of adverse events related to volume depletion (eg, dehydration, hypovolemia, hypotension, orthostatic hypotension, syncope, postural dizziness). These events occurred at higher frequency and were more pronounced in some populations. As SGLT2 inhibition can lead to volume depletion, there is a concern for potential adverse renal effects. In clinical trials with marketed SGLT2 inhibitors, early declines in the estimated glomerular filtration rate (eGFR) were seen, although there was a return toward baseline levels over time during treatment and upon discontinuation of therapy. This early eGFR decline is believed to be related to dehydration and not due to progressing renal insufficiency. However, the pattern of eGFR decline appeared to be different in subjects with varying degrees of baseline renal function, with greater persistence of eGFR decline in subjects with moderate renal impairment. In addition, in subjects with moderate renal impairment there was a slightly higher incidence of renally-related adverse events reported in subjects receiving SGLT2 inhibitors than in controls.

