- **Objective:** To assess the effect on FPG of 5 mg ertugliflozin as compared with placebo.
- **Objective:** To assess the effect on time to first occurrence of a subject requiring glycemic rescue therapy during the first 18 weeks of 15 mg ertugliflozin as compared with placebo.
- **Objective:** To assess the effect on time to first occurrence of a subject requiring glycemic rescue therapy during the first 18 weeks of 5 mg ertugliflozin as compared with placebo.
- **Objective:** To assess the effect on the time to initiation of insulin for subjects not on insulin at randomization of 15 mg ertugliflozin as compared with placebo.
- **Objective:** To assess the effect on the time to initiation of insulin for subjects not on insulin at randomization of 5 mg ertugliflozin as compared with placebo.
- **Objective:** To assess the change in insulin dose over time for subjects receiving insulin at the time of randomization of 15 mg ertugliflozin as compared with placebo.
- **Objective:** To assess the change in insulin dose over time for subjects receiving insulin at the time of randomization of 5 mg ertugliflozin as compared with placebo.
- **Objective:** To assess the effect on body weight of 15 mg ertugliflozin as compared with placebo.
- **Objective:** To assess the effect on body weight of 5 mg ertugliflozin as compared with placebo.

- **Objective:** To assess the effect on the incidence of HbA1c <7% (53 mmol/mol) of 15 mg ertugliflozin as compared with placebo.
- **Objective:** To assess the effect on the incidence of HbA1c <7% (53 mmol/mol) of 5 mg ertugliflozin as compared with placebo.
- **Objective:** To assess the effect on the incidence of HbA1c of <6.5% (48 mmol/mol) of 15 mg ertugliflozin as compared with placebo.
- **Objective:** To assess the effect on the incidence of HbA1c <6.5% (48 mmol/mol) of 5 mg ertugliflozin as compared with placebo.
- **Objective:** To assess the effect on systolic blood pressure of 15 mg ertugliflozin as compared with placebo.
- **Objective:** To assess the effect on systolic blood pressure of 5 mg ertugliflozin as compared with placebo.
- **Objective:** To assess the effect on diastolic blood pressure of 15 mg ertugliflozin as compared with placebo.
- **Objective:** To assess the effect on diastolic blood pressure of 5 mg ertugliflozin as compared with placebo.
- **Objective:** To assess the effect on renal function of 15 mg ertugliflozin as compared with placebo.

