- **Objective:** To assess the effect on renal function of 5 mg ertugliflozin as compared with placebo.

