2.6.2. Secondary Endpoints

- Time to first occurrence of:
 - Cardiovascular death or hospitalization for heart failure;
 - Cardiovascular death;
 - MACE plus;
 - Fatal or non-fatal myocardial infarction;
 - Fatal or non-fatal stroke;
 - Hospitalization for heart failure;
 - Individual components of MACE (cardiovascular death, non-fatal myocardial infarction, non-fatal stroke).

- All-cause mortality.
- All MACE events (ie, not censored at the time of the first event).
- All cardiovascular death or hospitalizations for heart failure (ie, not censored at the time of the first event).
- Time to first occurrence of the composite of renal death, renal dialysis/transplant, or $\geq 2x$ increase in baseline serum creatinine.

When added to usual background therapy in subjects with T2DM and established vascular disease:

- Change from Baseline in HbA1c at Week 18, Week 52 and annually thereafter.
- Proportion of subjects with HbA1c $< 7\%$ (53 mmol/mol) and $< 6.5\%$ (48 mmol/mol) at 12, 24 and 36 months and annually thereafter.
- Time to the first occurrence of a subject receiving glycemic rescue therapy during the first 18 weeks of the study.
- Time to initiation of insulin for subjects not on insulin at randomization.
- Change in insulin dose from Baseline at Week 18, Week 52 and annually thereafter.
- Change from Baseline in systolic and diastolic blood pressure at Week 18, Week 52 and annually thereafter.
- Change from Baseline in body weight at Week 18, Week 52 and annually thereafter.
- Change from Baseline in eGFR and serum creatinine at Week 18, Week 52 and annually thereafter.
- Change from Baseline in albuminuria as measured by the urinary albumin to creatinine ratio at Week 18, Week 52 and annually thereafter stratified by albuminuria category at baseline (normoalbuminuria, microalbuminuria and macroalbuminuria).
- Progression of nephropathy as measured by the progression of normoalbuminuria to microalbuminuria and/or macroalbuminuria as well as measurement of regression of albuminuria (eg, macroalbuminuria \rightarrow microalbuminuria).

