6.4. Follow-up Phone Call

Each randomized subject should have a follow-up phone call 14 days after the last dose of investigational product to assess for AEs, SAEs and collect information on clinical events ([Section 7.1](#)), if applicable. The phone call should be completed within a ± 3 day window.

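### The per-dose renal-function objectives have no between-arm analysis: change in eGFR and creatinine is left to descriptive summaries

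*Protocol*

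**What the plan says.** Protocol Section 2.1.2 has one objective per dose: "To assess the effect on renal function of 15 mg ertugliflozin as compared with placebo" and "To assess the effect on renal function of 5 mg ertugliflozin as compared with placebo". The matching endpoint in Section 2.6.2 is "Change from Baseline in eGFR and serum creatinine at Week 18, Week 52 and annually thereafter". The Study Design part of the Protocol Summary names renal function and albuminuria as separate items ("glycemic control, blood pressure, body weight, renal function and albuminuria"), so these objectives point to eGFR and creatinine, not to the urinary albumin:creatinine ratio.

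On analysis, Section 9.4 states: "Continuous endpoints (HbA1c, FPG, body weight, systolic blood pressure and diastolic blood pressure) will be analyzed using a constrained longitudinal data analysis (cLDA) model". That model delivers least-squares mean differences with 95% confidence intervals. What is not on the list is covered by one sentence: "Other continuous endpoints will be summarized with descriptive statistics by treatment and time".

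On the expected course, Section 1.2.2 reports that with the marketed drugs of this class "early declines in the estimated glomerular filtration rate (eGFR) were seen, although there was a return toward baseline levels over time during treatment". It adds that eGFR also moved back toward baseline after stopping, and that the decline persisted more in moderate renal impairment.

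**The concern.** An objective framed as a comparison with placebo needs an estimate of the difference and a measure of its uncertainty. Arm-by-arm means supply neither.

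Two features make this more than a missing detail. First, the protocol expects an early eGFR fall followed by some recovery, so the reader needs the between-arm difference at successive visits, with intervals, to tell an early step from a later trend. Second, the descriptive method is the weaker one when data are incomplete. Section 6.6 lets subjects who stop study drug choose phone contact only, which brings no chemistry sample, and Section 9.1 assumes 5% withdrawal a year. Observed means at late visits describe those who still attend. A likelihood-based longitudinal model uses each subject's earlier values and is valid under the less demanding missing-at-random assumption.

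**Working it through.** **1. Is there a plan figure to reproduce?** None for eGFR or creatinine change: the documents give no SD, effect size or power for them. The nearest renal figure is the power for the renal composite in Section 9.1: 79% with 144 and 190 events at a true HR of 0.65. With 2:1 allocation the drift is √(events × 1/3 × 2/3) × |ln 0.65|.
- Interim: √(144 × 2/9) × 0.431 = 2.44, against a critical value of 2.33 (two-sided 2.0%).
- Final: √(190 × 2/9) × 0.431 = 2.80, against 2.01 (two-sided 4.4%).
- With correlation √(144/190) = 0.87, the overall power is 79.2%.

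That figure is sound, but it concerns a pooled-dose event endpoint and not eGFR over time.

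**2. Where could a between-arm eGFR analysis sit?**

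| Place | What it provides | eGFR or creatinine contrast? |
|---|---|---|
| Protocol 9.3 | Cox models for time-to-event endpoints, including the renal composite | No; events only |
| Protocol 9.4, cLDA | HbA1c, FPG, weight, systolic and diastolic pressure | No; not listed |
| Protocol 9.4, remainder | Descriptive statistics | No |
| Protocol 9.5.1 | Albuminuria, compared between ertugliflozin and placebo | No |
| Protocol 9.6 | Descriptive summaries of laboratory changes | No |
| SAP Appendix 2, primary SAP excerpts | Cox and Andersen-Gill analyses; per-dose hazard ratios for MACE and the tested endpoints | No |

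The objectives for body weight and blood pressure in Section 2.1.2 have the same form as those for renal function, and they do receive a modelled contrast.

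**3. Are the data there?** Yes. The Schedule of Activities takes the chemistry group at every clinic visit: Weeks 6, 12, 18, 26, 39 and 52, then every four months. Table 4 in Section 7.9 includes serum creatinine and eGFR in that group.

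**4. What would the model add?** The 95% half-width for one dose against placebo at one visit is about 1.96 × SD × √(2/n). Per arm, n = 8000/3 ≈ 2667. The SD of eGFR change is not in the documents; 10 to 15 mL/min/1.73 m² is assumed. The case of 1500 per arm is an assumed late-visit number.

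| n per arm | SD 10 | SD 15 |
|---|---|---|
| 2667 | 0.54 | 0.81 |
| 1500 | 0.72 | 1.07 |

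The simple formula ignores any gain from correlation between visits. Under these assumptions the trial can estimate the per-dose difference to within roughly 0.5 to 1.1 mL/min/1.73 m².

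**The case against.** The strongest reply is that the governing document is not in hand. Section 9 of the protocol is an outline that the SAP may modify. The SAP supplied is a heart-failure supplement that only excerpts the primary SAP, so an eGFR model may exist there. This stands, and it is why confirmation comes first in the fix.

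Next, the objectives are to assess, without a hypothesis, and descriptive summaries of randomised arms are a comparison of a kind. Change in insulin dose is treated the same way. Other renal evidence is compared between arms: the renal composite by Cox model, with per-dose hazard ratios in the primary SAP excerpt, and albuminuria. These points lower the stakes. They do not supply the per-dose effect on eGFR or creatinine.

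Three stronger readings are tempting, and the documents do not support them:

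- *Early and late change are pooled.* A reader might infer this because every on-treatment change from Day 1 contains the early drop. But results are shown visit by visit, so the time pattern stays visible. The cLDA contrast shares this feature, so it is not a fault peculiar to the descriptive method.
- *No off-drug eGFR will exist.* Section 6.4 plans only a call ("Each randomized subject should have a follow-up phone call 14 days after the last dose of investigational product"). However, subjects off drug may attend clinic visits (Section 6.6), end-of-study chemistry is done on or off drug (Section 6.3.3 and the Schedule of Activities notes), and Section 7.11 asks for repeat tests after renal discontinuation. What is missing is a systematic off-drug sample.
- *Ertugliflozin would look worse than placebo for a stated number of years.* If the drop is D and the yearly slope benefit is b, the curves cross at D/b. For an assumed D of 2 to 5 and b of 0.5 to 1.5, that runs from 2/1.5 = 1.3 years to 5/0.5 = 10 years. The protocol gives neither quantity, so this is illustration only.

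**Conclusion.** The concern holds in a limited form. In the documents supplied, the per-dose renal-function objectives have an endpoint but no between-arm estimate or confidence interval for it. A more informative analysis is already specified in the same section for objectives of the same form.

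The consequence is confined to secondary objectives without hypothesis tests; type I error control, the primary analysis and the renal composite are not affected. It would be too strong to say that the trial leaves renal function unexamined. What is lost is a quantified difference for each dose and a better treatment of missing values. The size given rests on the assumed SD and late-visit numbers, and the conclusion itself rests on the primary SAP not already containing such a model.

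**What to change.** First confirm whether the primary SAP already models eGFR and creatinine by dose. If it does, a cross-reference in Section 9.4 is enough.

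If it does not, add eGFR and serum creatinine to the endpoints analysed by cLDA in Section 9.4. Report the least-squares mean difference and 95% confidence interval for 5 mg and for 15 mg against placebo at each scheduled visit, including Week 6. The Week 6 contrast then shows the early change, and the later visits show what follows.

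A slope analysis may be added as supportive only. Any slope from Week 6 onward should stand beside the total slope from Day 1, with a caution on two sources of bias: recovery from the early drop can pass for slower decline, and subjects leave treatment selectively, since Section 6.7.4 ties discontinuation to a low confirmed eGFR.

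The cost is analysis wording and further runs of an existing model, with no new visits or samples. HbA1c is taken at the same post-randomisation visits, so the model is of a size already planned. The endpoint definition does not change. Section 9 requires an amendment for major changes to analyses, so the sponsor should judge whether this counts as one, and should date the wording before unblinding.

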with metformin. The number of subjects using background insulin in the overall study population enrolled in this trial will not be allowed to exceed approximately 50%. The primary endpoint of HbA1c change from Baseline will be measured at Week 18. Secondary endpoints include change from Baseline in FPG, body weight, the proportion of subjects with an HbA1c <7% (53 mmol/mol) at Week 18, change from Baseline in systolic and diastolic blood pressure at Week 18 and change from Baseline in insulin dose at Week 18. Details on the treatment for glycemic control can be found in [Section 5.5.1](#). After Week 18 subjects enrolled in the insulin with or without metformin sub-study will continue to participate in the main cardiovascular study.

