5.5.1. Treatment for Glycemic Control for Type 2 Diabetes

To enable an assessment of the glycemic effects of ertugliflozin (or dietary and exercise counseling alone for subjects randomized to placebo), doses of background AHA medications will be required to be held constant in **all** subjects enrolled in this trial for the initial 18 weeks of the trial **with two exceptions**:

First, subjects will be prescribed glycemic rescue therapy if they meet specific, progressively more stringent, glycemic thresholds (see Table 3) based on a **repeated, confirmed** FPG measured by the **central lab** according to the directions below. Subjects who require a repeat FPG to determine if they meet the criterion for glycemic rescue therapy should have the repeat FPG measurement performed as early as possible (within approximately 7 days following the receipt of initial test results).

Second, a subject experiencing clinically significant hypoglycemia according to the investigator at any time during the trial is permitted to have the dose of appropriate background AHA (eg, insulin, SU, glinide) reduced or discontinued as per the judgment of the investigator or the treating physician.

Choice and dosing of glycemic rescue will be at the discretion of the investigator or the treating physician and they will be responsible for managing the initiation and titration of the glycemic rescue therapy consistent with standards of care for management of patients with T2DM within the country of the investigational site. If glycemic rescue therapy is initiated by the investigator it can be initiated at a scheduled or unscheduled visit but not during a telephone call. For details on the Glycemic Rescue Visit see [Section 6.5](#).

Following the Week 18 visit (V5), the investigator/treating physician is able to make any changes in the subject's AHA treatment regimen to achieve an appropriate HbA1c level for the subject (with exception of prohibited concomitant medications listed in [Section 4.2](#)).

Details on the specific glycemic rescue criteria for the initial 18 weeks of the trial are provided in Table 3 below.

Table 3. Glycemic Rescue Criteria for All Subjects for the First 18 Weeks

Randomization through Week 6	FPG >270 mg/dL (15.0 mmol/L)
After Week 6 through Week 12	FPG >240 mg/dL (13.3 mmol/L)
After Week 12 through Week 18	FPG >200 mg/dL (11.1 mmol/L)

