This model assumes a common mean across treatment groups at baseline and a different mean for each treatment at each of the post-baseline time points. In this model, the response vector consists of baseline and the values observed at each post-baseline time point. Time is treated as a categorical variable so that no restriction is imposed on the trajectory of the means over time. No explicit imputation of missing assessments will be performed. The treatment difference in terms of mean change from baseline to the primary time point of Week 18 will be estimated and tested from this model using least-squares means and 95% confidence intervals. The two-sided p-value will also be provided for testing the significance of the difference between treatment groups. An unstructured covariance matrix will be used to model the correlation among repeated measurements. The Kenward-Roger adjustment will be used with restricted (or residual) maximum likelihood (REML) to make proper statistical inference. Sensitivity analyses will be planned to assess the robustness of the primary model. Descriptive and graphical summaries by treatment group and time point will also be presented.

The two primary hypotheses, comparisons of each ertugliflozin dose to placebo, will be tested sequentially to control the overall Type I error rate at 0.05. The 15 mg dose will be tested first, and the 5 mg dose will be tested if and only if a statistically significant result is achieved for 15 mg.

Secondary Efficacy Analyses: The proportion of subjects achieving an HbA1c <7% (53 mmol/mol) at Week 18 will be analyzed using a logistic regression model with terms for treatment (categorical), metformin use (yes/no; applicable for insulin with or without metformin sub-study only), Baseline eGFR, and Baseline HbA1c (continuous). Summary measures from the analysis will include the odds ratio, 95% confidence interval for the odds ratio, and p-value for the comparison of treatment groups.

090177e187d04317\Approved\Approved On: 14-Mar-2016 14:12

The secondary endpoints of fasting plasma glucose, body weight, and blood pressure will be analyzed separately by fitting constrained longitudinal data analysis models similar to that used for the primary endpoint. For the insulin with or without metformin sub-study, the change in insulin dose from Baseline to Week 18 will also be summarized.

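### The protocol sets comparative insulin-dose objectives but plans only descriptive statistics for them, which limits how HbA1c differences after Week 18 can be read

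*Protocol*

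**What the plan says.** **Objectives.** Protocol Section 2.1.2 includes, for the higher dose, this aim: "assess the change in insulin dose over time for subjects receiving insulin at the time of randomization of 15 mg ertugliflozin as compared with placebo". A matching objective follows for 5 mg. Neither carries a hypothesis.

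**Endpoint.** Section 2.6.2 lists "Change in insulin dose from Baseline at Week 18, Week 52 and annually thereafter".

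**Analysis, overall study.** Section 9.4: "Continuous endpoints (HbA1c, FPG, body weight, systolic blood pressure and diastolic blood pressure) will be analyzed using a constrained longitudinal data analysis (cLDA) model". That model yields mean treatment differences with 95% CIs. The next provision for continuous data is "Other continuous endpoints will be summarized with descriptive statistics by treatment and time".

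**Analysis, insulin sub-study.** Section 9.8 says "the change in insulin dose from Baseline to Week 18 will also be summarized". Insulin dose is not in that section's six-step testing sequence.

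**Background therapy.** Section 5.5.1 holds background anti-hyperglycemic (AHA) doses constant for the first 18 weeks, apart from glycemic rescue and reductions for hypoglycemia. After the Week 18 visit, "the investigator/treating physician is able to make any changes in the" subject's AHA regimen to reach an appropriate HbA1c, prohibited agents excepted.

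**The concern.** The two objectives ask how each dose compares with placebo, and the planned output does not make that comparison. By-arm summaries give no planned difference, no interval and no stated approach to missing values. They describe only subjects with a recorded dose at each visit, and Section 6.6 lets subjects off study drug attend annually only or be followed by telephone. If availability differs by arm, raw visit means drift apart for reasons other than treatment. The cLDA planned for neighbouring endpoints uses all observed values and is valid under missing at random.

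The gap matters most after Week 18. Once therapy is adjusted toward a glycemic goal, part of a drug effect can show as less insulin rather than lower HbA1c. A narrowing HbA1c difference at Week 52 or later could reflect a waning effect or more background therapy on placebo. An insulin-dose difference with an interval is one of the few results that would help a reader weigh these. The Week 18 sub-study summary cannot stand in for it, because doses are meant to be stable until then.

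**Working it through.** No figure in the protocol is in dispute, so the main check is textual.

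| Step | Place | Finding |
|---|---|---|
| Is the objective comparative? | Protocol 2.1.2 | Yes, 15 mg and 5 mg each against placebo |
| At what times? | 2.6.2 | Week 18, Week 52, yearly |
| In the modelled list? | 9.4 | No; HbA1c, FPG, body weight, systolic and diastolic pressure only |
| What does it get? | 9.4, remaining continuous endpoints | Descriptive statistics |
| Modelled in the sub-study? | 9.8 | No; summarized, and outside the testing sequence |
| Covered in the SAP? | SAP introduction and Appendix 2 | No; a heart failure supplement whose extracts from the primary SAP do not address insulin dose |

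The HbA1c, FPG, body weight and blood pressure objectives in Section 2.1.2 are worded the same way and also have no paired hypothesis, yet they receive a modelled difference. The wording therefore does not explain the different treatment.

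**Would a modelled comparison be informative?** Inputs from the protocol: about 8000 subjects randomized 1:1:1 (Section 5.1), and the cap in Section 3.2: "The number of subjects using background insulin in the overall study population enrolled in this trial will not be allowed to exceed approximately 50" percent. Assumed, because the documents give no values: 30–50% on insulin at randomization, 20–40% without a value at the visit, and an SD of change of 15–30 U/day.

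Subjects per arm: n = 8000 × share ÷ 3 × (1 − missing)
- Low: 8000 × 0.30 ÷ 3 × 0.60 = 480
- High: 8000 × 0.50 ÷ 3 × 0.80 = 1,067

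95% CI half-width for one dose against placebo: 1.96 × SD × √(2/n)
- Best case: 1.96 × 15 × √(2/1067) ≈ 1.3 U/day
- Worst case: 1.96 × 30 × √(2/480) ≈ 3.8 U/day

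Difference detectable with 90% power: 3.24 × SD × √(2/n)
- Best case: 3.24 × 15 × √(2/1067) ≈ 2.1 U/day
- Worst case: 3.24 × 30 × √(2/480) ≈ 6.3 U/day

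Without an assumed SD, the half-width is 1.96 × √(2/1067) ≈ 0.08 SD to 1.96 × √(2/480) ≈ 0.13 SD. This is the unadjusted two-sample formula, used as an approximation to the cLDA contrast. It shows only that the comparison is feasible at the planned sample size.

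**The case against.** **The effect is not wholly unestimated.** A reader might infer that insulin sparing is never estimated. The documents do not support that. Arm-level summaries allow a crude difference by subtraction and, if n and SD are tabulated, a hand-made interval. Section 2.6.2 also lists time to starting insulin in subjects not on it at randomization. On a plain reading of Section 9.3, whose list of time-to-event endpoints is given as examples, this gets a Cox hazard ratio and nominal 95% CI, although it is not named. This stands. What is missing is a planned, model-based comparison of dose in baseline insulin users.

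**HbA1c remains interpretable.** A reader might also infer that HbA1c differences after Week 18 cannot be interpreted. They can: Section 9.4 compares randomized arms, and the result is the effect of assignment with background therapy adjusted as needed. It does not isolate the drug's own glycemic effect.

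**Insulin dose is only part of the explanation.** Any permitted AHA may change after Week 18, and the cap leaves about half or more of the population outside the proposed model. The contrast would not by itself separate a waning effect from intensified background therapy. This stands and limits what the fix can deliver.

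**Descriptive handling may be deliberate.** The sub-study insulin-dose objectives in Section 2.2.2 have no hypotheses, unlike the other secondary objectives there, and insulin dose is outside the testing sequence. That supports leaving it untested. It does not explain a comparative objective with no planned estimate.

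**The primary SAP was not available.** Section 9 says a SAP gives further detail and may modify the methods, so a model may exist there. The same section says major modifications of endpoint analyses will also be reflected in a protocol amendment, and the current protocol text has none for this endpoint.

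**Conclusion.** The point holds as a mismatch between objective and analysis. Two comparative objectives in Section 2.1.2 are assigned a method in Section 9.4 that gives no treatment difference or confidence interval, and no available passage supplies one. The consequence is a limit on interpreting HbA1c after Week 18, not a bar to it.

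This is a secondary endpoint with no hypothesis and no place in any testing sequence; MACE, Type I error and sample size are untouched. It is worth correcting but sits at the low end of importance. The ±1.3 to ±3.8 U/day precision is illustrative: insulin share, missingness and SD are all assumed, and one missingness range is applied to every visit. The conclusion on the mismatch needs none of these assumptions, but it is confined to the available documents.

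**What to change.** In Protocol Section 9.4, add total daily insulin dose (U/day), in subjects on insulin at randomization, to the cLDA endpoint list. Analyse stopped insulin as 0 U/day. Report 15 mg versus placebo and 5 mg versus placebo differences with nominal 95% CIs at Week 18, Week 52 and yearly, labelled as supportive estimates outside the testing hierarchy. Showing them beside the HbA1c differences at the same visits would help, with a note that other AHAs may also have changed.

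The cost is one more model and a derivation rule for total daily dose. Section 5.5 records AHAs throughout the trial and asks about medication at each visit, but it permits reliance on subject report and does not define a total-daily-dose variable, so the rule needs care. If the sponsor intends insulin dose to be descriptive only, rewording the two objectives in Section 2.1.2 would remove the inconsistency, but it would leave the comparison unmade.
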